Patients will be randomly assigned to either a control or experimental group allocated in the ratio of 1:1 by use of a computer-generated randomization schedule. Patients will be stratified according to whether they have undergone lumpectomy or mastectomy. We will randomize the block size to between 4 and 8 patients per block. Each block will therefore consist of patients who have undergone either lumpectomy or mastectomy, allocated in a 1:1 ratio. Block size will be concealed to the investigators until the end of the trial (i.e. after data analysis and statistical evaluation). The allocation sequence will be generated by a staff member with no other involvement in the trial. Assignments will be placed in sequentially numbered, opaque, sealed envelopes with the randomization number printed on them. These envelopes will be packed by a staff member with no other involvement in the trial. Every assignment will contain a code that corresponds to tubes of the melatonin/DMSO or placebo preparation. The primary investigator will enroll and assign participants to intervention on the basis of the assignment code from the envelope. Envelopes as well as tubes with active and placebo cream will be stored in a locked cabinet at Rigshospitalet.

Outcome assessment will be performed by the primary investigator, who is blinded to treatment allocation. Participants are also blinded to treatment allocation. The primary investigator will be blinded when performing data analysis and statistical evaluations.

Should the investigator deem it necessary for the safety of the patient, the investigator can un-blind a patient. Treatment-allocation will be noted in a document on a secure folder on a drive on the server of the Region Hovedstaden. Should an investigator need to un-blind a patient, they can access this document from their computer. Treatment allocation will only be un-blinded if it is imperative to the treatment of the patient. The treatment allocation will in this case only be

revealed to one other investigator than the primary investigator. This investigator will oversee the treatment of the patient. Registration of adverse reactions is described in the “Harms” section.

Drop-outs and patient retention

We plan to promote participant retention and complete follow up by asking for contact information (phone number and e-mail) and preferred way of contact. We will schedule appointments with patients at same location, accommodating their calendar, as far as possible.

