calculation are based on the patients receiving breast-conserving therapy, on their last day of radiation. The 142 patients scored a breast symptom score mean (SD) of 82.2 (15.1).

Mean (SD) a*-value for breast symptoms: 82.2 (15.1)

We aim to reduce the breast symptom score to 70.

Alpha: 5%

Beta: 20%

Sample size needed: Two groups of 24, totaling 48 patients.

Because we have three sample size calculations, resulting in required sample sizes of 28, 16, and 48 patients, respectively, and when considering the risk of drop-outs, we estimate to include a total of approximately 80 patients. This is based on the inclusion schedule, where the required 48 evaluable patients finalizing all data for the outcome parameters have to be completed, will require an inclusion larger than 48 patients. This is because there will be 8 weeks from inclusion to obtaining the data point at two weeks after ended radiation therapy. Thus, we will include continuously in randomized blocks (see randomization above) until patient 48 has completed the 8 weeks data point. If we get less than 24 patients in one group completing the 8-weeks data point, additional blocks will be included, until we have at least 48 patients. The staff-member responsible for the randomization sequence will inform the investigators how many patients they will need to include to reach this point because of the randomization of the block size. During 2016, Rigshospitalet treated 194 patients who matched our inclusion criteria. Therefore we find it feasible to finish inclusion in approximately 6 months.

Statistical analyses

Normality of data will be assessed through visual inspection of histograms and Q-Q plots. Normally distributed data will be analyzed with parametric tests (e.g. unpaired t-tests), and not normally

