distributed data will be analyzed with non-parametric tests (e.g. Mann-Whitney U test). Our primary outcomes are the RTOG scores and the image analysis two weeks after the last radiation fraction, as well as the QLQ-BR3 breast symptoms on the last day of radiation therapy. Our secondary outcomes will be analyzed as follows: We will analyze steroid usage through two different outcomes. Days of steroid usage will be analyzed through either parametric or non-parametric tests. Any steroid usage (yes/no) will be analyzed through χ^2 or Fisher's Exact test. The RTOG scores, the quality of life questionnaires, and the image analysis values for the entire period will be analyzed in a mixed linear model, which takes correlation between patients into account. Subgroup analyses will be performed for mastectomized and lumpectomized patients respectively, if feasible. Other subgroup analyses may be performed based on background variables (fractionation schedule, histopathology and demographic data). Missing data will be taken into consideration when using the mixed linear model. A detailed statistical analysis plan will be formulated and be supervised by a bio-statistician prior to study start.

Data management

All outcomes will be collected by the primary investigator at time points listed in table 3. All data entered into the electronic case report form (eCRF) will be validated through “required fields” and format (e.g. date-format) where applicable. In the clinical photographs, patients will be marked with patient-ID written on tape, fixed to the patients’ chest. The time-stamp of the photograph will be noted in the eCRF. a*-values will be imported into the eCRF.

Our data will be stored electronically in Research Electronic Data Capture (REDCap), an electronic database used throughout the Capital Region of Denmark. All confidential data will be stored in a secure server for 15 years after patient enrollment in the study. Only the investigators and the Good Clinical Practice (GCP) Unit will have access to these data. After conclusion of the study, a final anonymized dataset will be available to RepoCeuticals ApS who has sponsored the

study through a grant through a formalized research contract between the Capital Region of Denmark and the company. Ownership of data is shared between the investigators and RepoCeuticals ApS.

Monitoring

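### Surgery-type subgroups are planned as separate analyses with no treatment-by-surgery interaction, so they cannot show whether the effect differs between lumpectomy and mastectomy patients

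*Combined protocol and SAP*

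**What the plan says.** The Statistical analyses section commits to one analysis per surgery group: "Subgroup analyses will be performed for mastectomized and lumpectomized patients respectively, if feasible". What would make this feasible is not defined. The next sentence is optional: "Other subgroup analyses may be performed based on background variables". It names three categories: fractionation schedule, histopathology and demographic data.

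Surgery type is the only stratification factor. Under Randomization and blinding: "Patients will be stratified according to whether they have undergone lumpectomy or mastectomy". The expected split between the two operations is not given.

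The methods named for group comparisons are the unpaired t-test or Mann-Whitney U test, the chi-square or Fisher's exact test for steroid use, and a mixed linear model for the whole period. No treatment-by-surgery term is mentioned for any of them. Further detail is deferred: "A detailed statistical analysis plan will be formulated and be supervised by a bio-statistician prior to study start". The combined document contains no such detailed plan.

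**The concern.** A difference in treatment effect between strata has to be estimated as a difference, with its own standard error. One analysis in each stratum gives two results at low and usually unequal power, and nothing that compares them. If one is significant and the other is not, a reader will tend to conclude that the cream works after one operation and not after the other, even when the true effect is the same in both.

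Because surgery type is the stratification factor, it is the subgroup readers will look at first. The trial is sized for about 80% power overall on the breast symptom score, so each stratum is underpowered on that outcome by construction. At stake is the interpretation of the subgroup results. The overall primary comparisons are not affected.

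**Working it through.** **Inputs from Sample size calculations.** Breast symptom score: control mean 82.2, SD 15.1, target 70, so the difference is 82.2 − 70 = 12.2. Alpha is 5%, taken as two-sided. There are 48 evaluable patients, about 80 included, allocated 1:1. The mean and SD come from one surgical group only: the data for this "calculation are based on the patients receiving breast-conserving therapy, on their last day of radiation".

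**Assumptions not in the documents.** The lumpectomy share is 50% to 80%. The same effect and SD hold in mastectomy patients.

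**Reproducing the plan's figure.** n per arm = 2 × (1.960 + 0.842)² × 15.1² / 12.2² = 24.05, against a stated 24. Power at 24 per arm is 79.9% by the normal approximation. A one-sided test would need only 19 per arm, so the two-sided reading fits.

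**Power within a stratum.** With n per arm, I used t-test power with 2n − 2 degrees of freedom and noncentrality (12.2/15.1) × √(n/2). Example at n = 12: 0.808 × 2.449 = 1.98, power 0.47.

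**Chance that exactly one stratum is significant under a uniform effect.** This is p₁(1 − p₂) + p₂(1 − p₁).

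| Evaluable | Lumpectomy share | Per arm (lump./mast.) | Power | Exactly one significant |
|---|---|---|---|---|
| 48 | 50% | 12 / 12 | 0.47 / 0.47 | 50% |
| 48 | 67% | 16 / 8 | 0.60 / 0.33 | 53% |
| 48 | 75% | 18 / 6 | 0.65 / 0.25 | 58% |
| 48 | 80% | 19.2 / 4.8 | 0.68 / 0.20 | 61% |
| 80 | 50% | 20 / 20 | 0.70 / 0.70 | 42% |
| 80 | 75% | 30 / 10 | 0.87 / 0.40 | 57% |
| 80 | 80% | 32 / 8 | 0.89 / 0.33 | 64% |

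**Sensitivity at 48 evaluable.**
- Half the breast symptom effect (6.1 points): power at an equal split is 0.157 per stratum, so 2 × 0.157 × 0.843 = 26%; at 80/20 it is 28%. About 27% throughout.
- No effect: 2 × 0.05 × 0.95 = 9.5%.
- RTOG (90% v 41%, normal approximation): 38% at an equal split, 64% at 80/20.
- a* value (18.4 v 13.44, difference 4.96), equal split: 5% with the root-mean-square of the two SDs (3.47 and 2.36), 15% with SD 3.47 in both arms. At 80/20 the first of these rises to 38%.

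**What an interaction test would do.** In simulated trials with a uniform breast symptom effect, it declared a difference in about 5%, as it should.

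**How precise the interaction would be.** SE = 15.1 × √(2/n_L + 2/n_M), where n_L and n_M are the numbers per arm in each stratum.
- 48 evaluable, equal split: 15.1 × √(2/12 + 2/12) = 8.72; times 2.015 (44 df) gives a 95% half-width of 17.6 points.
- 48 evaluable, 80/20: 15.1 × √(2/19.2 + 2/4.8) = 10.90; half-width 22.0 points.
- 80 evaluable, 70/30 (28 and 12 per arm): half-width 14.7 points.

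If the full 12.2 points existed in only one of two equal strata at 48 evaluable, 12.2/8.72 − 1.96 = −0.56, which gives power of about 29%. The difference in effects detectable with 80% power is 2.80 × 8.72 = 24.4 points.

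**The case against.** The strongest reply is that the harmful step is not written down. The plan sets no significance criterion within strata and no rule for claiming that effects differ. Presenting results by stratification factor is ordinary practice. A reader might infer that the plan will report a lumpectomy-only effect; the text does not say so. That part of the reply stands. It does not remove the problem, because separate analyses are the stated method and nothing else is offered for comparing the strata.

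Second, a detailed analysis plan is promised and may deal with this. Its content is unknown, so the promise neither cures nor worsens the gap. It is the natural place for the repair.

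Third, a reader might take the half-of-trials figure as general. It is not. It belongs to one of three primary outcomes, at the full planned effect, with an assumed surgery split and with an SD from breast-conserving patients applied to both strata.

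Fourth, it is tempting to count every row of Table 2 as a planned test and quote a large chance of some false positive. The text names three categories and makes them optional. Such a figure would also describe multiplicity, which an interaction term does not reduce.

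Last, the interaction test has low power. This is correct, and it is a reason for the exploratory label. It does not make separate tests informative about a difference.

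**Conclusion.** The point holds in a limited form. The plan specifies separate analyses by surgery type and leaves other subgroups open, with no interaction estimate and no exploratory label. Under a uniform effect on the breast symptom score, exactly one stratum would be significant in about 50% to 61% of trials at 48 evaluable, and in 42% to 64% if all 80 are evaluable. This assumes a difference of 12.2 with SD 15.1 in both strata and a 50% to 80% lumpectomy share. At 48 evaluable it falls to about 27% at half that effect, and to about 5% to 15% for a* at an equal split. The documents do not support a claim that the plan will infer a difference from two p-values, or that the same percentage applies to all outcomes. The weakness affects secondary analyses, but it is cheap to correct and should be corrected.

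**What to change.** In the detailed analysis plan:

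1. For each primary outcome, estimate the treatment-by-surgery interaction and report it with its 95% CI. The primary comparisons are two-group tests with no model for the term to enter, so name one. Examples are a linear model with treatment, surgery type and their product at the primary time point, or the product term in the mixed linear model already planned.
2. Show the effect in each surgery stratum with its CI, and make no significance claim within a stratum.
3. List any other subgroups in advance and label them exploratory.
4. State that a non-significant interaction will not be read as evidence of a uniform effect.

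The cost is analysis-plan wording and one model term per outcome. No extra patients or data are needed, since surgery type must be known for randomization. The drawback is imprecision: at 48 evaluable the half-width of about 18 to 22 points exceeds the 12.2-point target, so the interval will usually be compatible with both no difference and a large one.

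### The tests implied for the RTOG and a* primaries drop patients who miss follow-up week 2, while the model that handles missing data is only secondary: minor, and cheap to fix

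*Combined protocol and SAP*

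**What the plan says.** The Statistical analyses section sets the time point: "Our primary outcomes are the RTOG scores and the image analysis two weeks after the last radiation fraction". The third primary, QLQ-BR23 breast symptoms, is read on the last day of radiation.

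The tests come in a general statement just before this: "Normally distributed data will be analyzed with parametric tests (e.g. unpaired t-tests", with Mann-Whitney as the example for non-normal data. Neither is tied to a named outcome. After the lead-in "Our secondary outcomes will be analyzed as follows", the section adds that RTOG, quality of life and "the image analysis values for the entire period will be analyzed in a mixed linear model", "which takes correlation between patients into account". The missing-data sentence, "Missing data will be taken into consideration when using the mixed linear model", refers to that model only. Further detail is deferred: "A detailed statistical analysis plan will be formulated and be supervised by a bio-statistician prior to study start". That plan is not in the supplied text.

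The Drop-outs and patient retention section foresees patients who do not want all three follow-up visits. It lets them complete the two questionnaires and the steroid items electronically; RTOG scoring and photographs are not on that list. The same section promises that data from drop-outs will all enter the analyses. Under Sample size calculations, "the required 48 evaluable patients finalizing all data for the outcome parameters have to be completed", and blocks are added until each group has at least 24 patients with the week-2 value.

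**The concern.** A single-visit test with no imputation uses only patients who attended that visit. If attendance is related to skin condition, it compares selected groups, and it ignores the weekly scores and photographs already collected from the absentees. The promise to use all drop-out data is then not kept by the implied primary tests for these two outcomes. Adding blocks restores the head count, but the added patients are again selected by attendance.

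The analysis that could use the partial data is planned on the same measurements but is not designated primary. Its description also names the wrong correlation: repeated weekly values need correlation within patient.

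At stake are some bias in two of the three primaries and an unnamed estimator. Sample size is not at stake.

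**Working it through.** **Plan's own figures.** RTOG 90% vs 41%, two-sided 5%, 80% power, pooled variance: 14 per group, as stated. a* 18.4 vs 13.44 with SD 3.47: 8 per group, as stated. With 24 per group holding a week-2 value, normal-approximation power is 97% for RTOG and 99.9% for a*. Power is therefore not the problem.

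**Assumptions (none in the documents).** The correlation between follow-up weeks 1 and 2 is 0.6. A patient whose week-1 a* is more than 0.5 placebo SD below the placebo mean skips week 2 with probability s = 0.40 (0.60 in brackets below); others skip with probability 0.05. The rule is the same in both arms.

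**a*, closed form, in placebo SDs.** The true difference is (18.4 − 13.44)/3.47 = 1.429 and the SD ratio is 2.36/3.47 = 0.680. For an arm with mean μ and SD σ, let z = (−0.5 − μ)/σ. The missing share is m = 0.05 + (s − 0.05)Φ(z). The attenders' mean shifts upward by 0.6·σ·(s − 0.05)·φ(z)/(1 − m).

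- Placebo: z = −0.5, Φ = 0.309, φ = 0.352. m = 0.05 + 0.35 × 0.309 = 0.158. Shift = 0.6 × 0.35 × 0.352/0.842 = 0.088.
- Melatonin: z = (−0.5 + 1.429)/0.680 = 1.366, Φ = 0.914, φ = 0.157. m = 0.05 + 0.35 × 0.914 = 0.370. Shift = 0.6 × 0.680 × 0.35 × 0.157/0.630 = 0.036.
- Attenders only: 1.429 + 0.088 − 0.036 ≈ 1.48 (1.50) SD, or 5.14 (5.20) a* units against 4.96. This is 4% (5%) too large.
- With SD 3.47 in both arms: 1.44 (1.41) SD, within 2% of the truth.

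**a*, simulation.** There were 10,000 trials per scenario, with enrolment until 24 attenders per arm.

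| Scenario | Attenders only | Mixed-model-type contrast |
|---|---|---|
| Protocol effect 1.43, protocol SDs | 1.48 (1.50) | 1.43 (1.43) |
| Protocol effect 1.43, equal SDs | 1.43 (1.41) | 1.42 (1.43) |
| Protocol effect and SDs, week 1 also missed | 1.48 (1.50) | 1.47 (1.49) |
| Illustrative effect 0.70 | 0.68 (0.65) | 0.70 (0.70) |
| No effect, same rule: rejection | 4.6% (4.9%) | 4.6% (4.6%) |
| No effect, melatonin 60%/5%, placebo flat 10% | −0.15 SD, rejection 8.3% | −0.01 SD, 4.5% |

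At the protocol effect, power is at least 99.8% under the same rule. In the last row, 7.7 of the 8.3 points favour placebo. When week 1 is missed too, the model removes (1.484 − 1.467)/(1.484 − 1.429) = 31% of the bias. At 0.70 SD it removes (0.688 − 0.679)/(0.700 − 0.679) = 43%.

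**RTOG.** Take grade 1 or higher at 90% vs 41% in both weeks, and s = 0.40 if the week before was grade 0, else 0.05. With latent correlation 0.6, the share moving from grade 0 to grade 1 or higher is 0.061 (placebo) and 0.1435 (melatonin).

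- Placebo attenders: (0.061 × 0.60 + 0.839 × 0.95)/0.915 = 91.1%.
- Melatonin attenders: (0.1435 × 0.60 + 0.2665 × 0.95)/0.7435 = 45.6%.
- Difference: 45.5 points, or 42.1 at s = 0.60, against 49. Exact Fisher power at 24 per group is 92% (89%), against 95% with none missing.
- Over correlations 0.4 to 0.8: 39 to 47 points, power 86% to 93%.
- If worse patients skip more (30% vs 5%): 50 to 52 points.

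**The case against.** The strongest reply is that these numbers show little harm, and that stands. At the protocol's effect a* is off by 0 to 5%, power is intact and type I error is nominal. The skip rates are assumed. The 60% case leaves about 55% missing on melatonin, so 24 attenders would need 24/0.447 ≈ 54 per arm, or about 107 patients, beyond the planned 80 or so. The 40% case (24/0.630 ≈ 38 per arm) fits. The simulation also stops at 24 per arm, whereas the protocol lets patients already included finish, so the real sample would be somewhat larger. Power of 66% to 67% at 0.70 SD is no evidence of loss: 24 per arm with no missing data gives 66%.

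The RTOG figures rest on a binary Fisher comparison that the plan does not assign to RTOG. The largest same-rule bias is in RTOG, where the fix leaves the primary comparison at week 2 among attenders. That is deliberate, because grades may be too sparse for a model-based primary. The promised detailed plan might already settle the matter; if so, the sponsor need only point to it.

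Three stronger readings are tempting.

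- A reader might infer that the requirement for 48 completers defines a completers-only analysis set that contradicts the drop-out promise. It is a recruitment rule. The promise can be met by the whole-period mixed model; it is only the implied primary tests that do not meet it.
- A reader might infer that the plan prescribes a completers' t-test for the primaries. It names no test for them; the order of sentences only implies one.
- A reader might infer a serious false-positive risk. If one arm lost its worst patients and the other lost patients at random, type I error would be about 7% to 10% at 10% missing and 16% to 27% at 30%. That is a stress test, and nothing in the documents suggests such a pattern. Patients and assessor are blinded. The placebo lacks DMSO and a garlic-like odour is a listed reaction, so some patients could guess their arm, but the documents do not show how many.

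**Conclusion.** The gap is real and minor. Two primaries sit at a visit that can be skipped, the implied tests discard those who skip it, and the only analysis with a missing-data statement is secondary and described with the wrong correlation. Under one skip rule for both arms, the a* error is at most about 5% at the protocol's effect. RTOG may be understated by roughly 2 to 10 points if milder patients skip, or overstated by 1 to 3 if worse patients do. Power stays above 80%, and type I error for a* stays near 5%. Material bias needs skipping that depends on both skin condition and arm; in the case tested it runs against melatonin.

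All sizes depend on assumed skip rates and correlations. The QLQ-BR23 primary, read on the last radiation day, is not affected.

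**What to change.** - **a\*:** make the treatment contrast at follow-up week 2 from the planned mixed model the primary estimate. Include all randomised patients with any post-baseline value, within-patient correlation, treatment-by-visit terms, baseline a* and surgery type. Count visits from the last fraction, so that courses of 15 to 30 fractions align. Keep the single-visit test as a sensitivity analysis.
- **RTOG:** name the week-2 comparison as primary, stratify it by surgery type and report week-2 attendance by arm. Add a sensitivity analysis that brings in non-attenders through their earlier weekly scores.
- **QLQ-BR23:** no change.
- **Wording:** correct the description of the correlation to within patient.

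The cost is wording in the analysis plan; no visits or patients are added. The downside is that the a* primary becomes model-based and assumes missing at random. It recovers less than half of the bias if follow-up week 1 is missed as well. It stays biased if skipping depends on the unseen week-2 value itself: 0.63 against a true 0.70 SD, with attenders only at 0.60. The RTOG sensitivity analysis may be fragile at about 24 completers per group.
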